6.5 N/A

6.6 N/A

## 7.0 Data and Specimen Banking

7.1 N/A

7.2 Participants who enroll in this study will be given the opportunity to have their de-identified data rolled into the Department of Surgery Data Repository (DSDR) IRB# 18020079. We will continue to protect and safeguard study data under the provisions of the DSDR.

7.3 N/A

7.4 N/A

7.5 N/A

## 8.0 Genetic Analysis Information

N/A

## 9.0 Sharing of Results with Subjects

N/A

## 10.0 Study Timelines

- An individual subject's participation in the study will comprise of one study procedure (contrast enhanced ultrasound will take 10 to 20 minutes total) we anticipate study duration will take approximately 30-60 minutes in length. Additionally data generating from SOC will be obtained from chart.
- Assuming an accrual rate of 15-20 subjects per month, we estimate enrollment will take 12-15 months to enroll 250 subjects.
- The Approximate study end date will be 3 years after IRB approval.

## 11.0 Inclusion and Exclusion Criteria

### Inclusion Criteria

- Present to Children's Mercy Adele Hall campus with a clinical concern for acute appendicitis
- Age 8 through 17 years
- seen between IRB approval date and 12/31/2020
- Has had an IV catheter placed as part of their standard of care

Exclusion Criteria

- Known cardiac abnormality
- Pulmonary hypertension
- Known sensitivity to sulfur hexafluoride, polyethylene glycol 4000, distearoylphosphatidylcholine (DSPC), dipalmitoylphosphatidylglycerol sodium (DPPG-Na), or palmitic acid
- Does not have an IV catheter placed
- Unable to roll over
- Unable to assent
- Pregnant
- Lactating
- Received an ultrasound image from an OSH

*11.1 These patients will be excluded from the study*

- Adults unable to consent
- Pregnant women
- Prisoners
- Wards of the state

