**14.0 Screening and Recruitment Methods**

*14.1 Potential subjects will be recruited in their hospital room, ED, or radiology department by a member of the general surgery team. Per standard of care, the general surgery team will be alerted by the emergency department when*

a patient presents with concern for acute appendicitis. The general surgery staff will screen for eligibility criteria. Those meeting all inclusion and no exclusion criteria will be invited to participate. PAC will be obtained on either a paper or electronic form.

- 14.2 The source of subjects will be the CMH Adele Hall campus emergency department.
- 14.3 Potential subjects will be identified when, per standard of care, the general surgery team is alerted by emergency department staff of a patient presents with concern for acute appendicitis. The general surgery staff will screen for eligibility criteria. Those meeting all inclusion and no exclusion criteria will be invited to participate.
- 14.4 A pre-screening log will be maintained for the purpose of tracking enrollment. Patients who are referred to the department of surgery for concern of acute appendicitis will have the date of referral, DOB, MRN, PAS, whether or not they met inclusion, were approached for participation and their choice to participate recorded on the pre-screen log. We are requesting a Waiver of HIPAA Authorization for recruitment purposes only. The PHI recorded on the screening log will help ensure required reporting elements at time of study publication, including the percentage of eligible patients enrolled and reasons patients decline enrollment. The pre-screen log will be destroyed at the conclusion of the study.

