## 17.0 Risks to Subjects

17.1 As part of SOC, all patients enrolling in this study will have at least one functioning intravenous catheter placed during the SOC blood draw, hence no new IV access will be required. We expect that there may be some mild discomfort related to the performance of the ultrasound study itself and will monitor for this. Other than the discomfort from the ultrasound probe, we do not expect any other ultrasound-related discomfort. Patients will be monitored by licensed personnel during the study interval. Per standard of care, patients will return to the ED while the results of their gray scale ultrasound and CT, if one was taken, are obtained. ED staff will continue to monitor patients for any adverse event.

Reported risks related to Lumason administration include:

Adverse Reaction	Number	(%)
Any Adverse Reaction	340	5
Headache	65	1
Nausea	37	0.5
Dysgeusia	29	0.4
Injection site pain	23	0.3
Feeling hot	18	0.3
Chest discomfort	17	0.2
Chest pain	12	0.2
Dizziness	11	0.2
Injection site warmth	11	0.2

Serious cardiopulmonary reactions, including fatalities, have occurred uncommonly in adults during or shortly following administration of ultrasound contrast agents, including Lumason. These reactions typically occurred within 30 minutes of administration. Hypersensitivity reactions such as skin erythema, rash, urticaria, flushing, throat tightness, dyspnea, or anaphylactic shock have uncommonly been observed following the injection of Lumason. The exclusion criteria eliminate any subjects with a known cardiac abnormality or a known sensitivity to sulfur hexafluoride, so we do not anticipate that these reactions will occur. Resuscitation personnel and equipment will be available during the study treatment and follow-up period.

17.2 This study poses a minor increase over minimal risk as Lumason will be used off-label, but the intervention presents an experience that is reasonably commensurate with those inherent to the subject's medical situation. The only risks attributable to the study are those

of the adverse reactions listed above, as these patients will have already had an IV placed, and would have ultrasound as part of their appendicitis workup. Furthermore, Lumason is currently FDA approved, and in use at CMH, for other abdominal CEUS applications such liver lesions and vesicoureteral reflux in pediatrics.

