## **25.0 Permission/Accent/Consent Process**

25.1 Permission/assent will be obtained on all subjects wishing to participate.

- The p/a process will take place in the ED at the patient's bedside.

- While eligible candidates will be given all necessary information to make an informed decision and will have every opportunity to ask questions, the waiting period available between informing the prospective subject and obtaining p/a will be limited as this study does not intend to delay standard of care treatment. A potential subject who has not affirmatively signed the p/a form prior to the standard gray scale ultrasound will continue through SOC treatment without prejudice.
- We will be following CMH research policies on informed consent.
- We will not be obtaining permission/assent via telephone as such is not feasible for this study.
- This pediatric research study will be conducted entirely in the state of Missouri and will involve enrolling minors under the age of 18.
- Parental permission will be obtained from one parent or LAR.
- Other than biological parents, LARs such as an adoptive parent will be allowed to consent for a child's participation in this study.
- Assent will be obtained from all children participating in this study unless the study team member attempting to obtain P/A determines the child is not capable of providing assent.
- The child's assent will be documented on the combined P/A form.
- In the event assent may not be obtained, the reason(s) will be documented in the provided section of the P/A form.

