#### Consent at 18 years of age, when minor subjects become adults

We are requesting a Waiver of Consent at Age 18. Active participation of the subject will be concluded, as this is a single-visit ultrasound study. Data collection will be completed before the subject turns 18. Data analysis might continue after some subjects have turned 18, but this is explained in the Permission/Accent form they would have signed at the time of enrollment. Furthermore, re-consenting at age 18 would be impracticable for this study, as these subjects will be emergency appendicitis patients at CMH, and most will be unlikely to return for follow up appointments after reaching 18.

Waiver or Alteration of Parental Permission or Child Assent Process (permission and/or assent will not be obtained, required information will not be disclosed, or the research involves deception)

N/A

Waiver or Alteration of Consent Process (consent will not be obtained, required information will not be disclosed, or the research involves deception)

N/A

Non-English Speaking Subjects

N/A

Cognitively Impaired Adults

N/A

Adults Unable to Consent

N/A

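### Section 11.0 excludes a child who cannot assent, but section 25.1 implies that a participating child judged incapable of assent may go on without it

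*Protocol*

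**What the plan says.** Section 11.0 gives "Unable to assent" as an exclusion criterion, without qualification. Sections 14.1 and 14.3 make the exclusions binding on recruitment: "Those meeting all inclusion and no exclusion criteria will be invited to participate".

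Section 25.1 covers the permission/assent (P/A) process at the bedside. Its opening line has permission/assent obtained for everyone who wishes to take part. A later bullet reads "Assent will be obtained from all children participating in this study unless the study team member" seeking it "determines the child is not capable of providing assent". The last bullet adds: "In the event assent may not be obtained, the reason(s) will be documented in the provided section of the P/A form".

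Further on in section 25.0, the entry headed "Waiver or Alteration of Parental Permission or Child Assent Process" is marked N/A, so no waiver of assent is requested. Section 17.2 describes the risk: "This study poses a minor increase over minimal risk as Lumason will be used off-label".

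**The concern.** Two parts of the protocol deal with the same child in different ways. Under section 11.0 a child who cannot assent is out of the study. Under section 25.1 a child judged incapable of assent appears as a participant for whom assent is simply not obtained and the reason is written down.

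Assent is one of the stated protections for children aged 8 to 17 who receive an intravenous contrast agent outside its approved indications. The situation is foreseeable: recruitment takes place in an emergency department, the revision history extends enrolment to 24 hours a day, and section 25.1 itself says that the time for the decision is limited. A team member who followed 25.1 literally could proceed, on one parent's permission, with a child whom the eligibility criteria exclude.

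**Working it through.** No figure in the protocol depends on this point and no arithmetic applies. The check is whether the passages can all be followed for one child.

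| Place in the protocol | Effect for a child who cannot assent |
|---|---|
| 11.0, exclusion criteria | Excluded |
| 14.1 and 14.3 | Not invited, because an exclusion is met |
| 25.1, opening line | Permission/assent is obtained for all who wish to take part; no exception at this point |
| 25.1, assent bullet | Exempt from the assent requirement that applies to participating children |
| 25.1, last bullet | Reason recorded on the P/A form; no statement that the child is then ineligible |
| 25.0, waiver or alteration of child assent | N/A; none requested |

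1. **Whom the exception covers.** The assent bullet is about children taking part in the study. Its exception therefore describes participants without assent. A child capable of assent does not need it, and a child not capable of assent is excluded by section 11.0. Read with section 11.0, the exception covers no eligible child.

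2. **What the documentation bullet means.** Read alone, it could be a record of why a child was not enrolled. It follows the exception for participating children, however, and the reason is entered on the form that documents permission and assent. Nothing in 25.1 turns the entry into a reason for stopping.

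3. **Order of events.** Staff screen against section 11.0 and invite those who pass. Under 25.1, incapacity is judged by the person who is trying to obtain permission/assent, which comes after invitation. Incapacity recognised only then has passed the screen, and the text in force at that moment is 25.1.

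4. **Whether another passage settles it.** Section 12.1 says only that provisions for soliciting assent are adequate. The N/A entry agrees with section 11.0 and leaves the exception without a matching request. No passage says which section prevails.

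**The case against.** The strongest reply is that the protocol taken as a whole already points to exclusion. Section 11.0 is unqualified, section 14.0 applies it before anyone is invited, 25.1 opens with a general requirement, and no waiver of assent is sought. Section 25.1 also sends a potential subject who has not signed the P/A form before the gray-scale scan on to standard care. On this view the exception is leftover consent wording and not a second eligibility rule.

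Much of that stands, and it is why the fix below leans towards section 11.0. It does not close the gap. The signing rule sits a few lines from the exception and concerns a form that combines parental permission with the child's assent; it does not say what happens when the parent signs and the child cannot. Leftover wording is still current text, and section 28.1 expects every team member to have read the protocol.

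Four stronger readings are tempting, and the protocol does not support them:

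- A reader might infer that 25.1 states that these children will be enrolled and given contrast. It does not; that is an implication of its wording.
- A reader might infer damage to the efficacy or safety results. The protocol gives no rule on deviations or analysis sets that would show this, and nothing links capacity to assent with the blinded radiologist's reading of enhancement.
- A reader might infer that a child's recorded inclusion status depends on which section the screener consulted. Section 14.0 has staff screen against the eligibility criteria, which are in section 11.0; 25.1 defines no inclusion status.
- A reader might treat a child who declines as excluded too. Refusal is not inability, and section 11.0 has no such criterion.

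**Conclusion.** The inconsistency is real and should be corrected. Section 11.0, section 14.0 and the N/A entry exclude a child who cannot assent. The exception in 25.1 implies that such a child may take part without assent, and nothing states which governs. The exposed case is narrow: a child who passes screening and is found incapable of assent when permission/assent is sought.

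The number of such children cannot be derived from the protocol. It is probably small, but that is a judgement and not a calculation. The point concerns participant protection and consistent eligibility. It changes no stated figure, and no effect on the endpoint estimates is shown. The conclusion rests on reading the 25.1 exception as applying to participants, which is what its wording says.

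**What to change.** Reconcile section 11.0, section 25.1 and the waiver entry in section 25.0. Because section 11.0, section 14.0 and the N/A entry agree, the consistent change is to:

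- remove from 25.1 the exception for children judged not capable of assent;
- replace the bullet on recording the reason with a statement that a child found unable to assent at the permission/assent step is ineligible under section 11.0 and does not receive the study CEUS;
- record that child on the pre-screen log as not eligible.

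If the sponsor does intend to enrol children who cannot assent, the exclusion in section 11.0 and the N/A entry must change instead.

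Either way, a child who is able to assent but declines should stay logged as eligible and declined. Section 14.4 already records the choice to participate separately from whether inclusion was met, and it wants the percentage of eligible patients enrolled and the reasons for declining to be reportable. Merging refusals with ineligibility would distort that percentage.

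The cost is a short amendment to 25.1. The P/A form may need a matching edit, but it is not shown, so that part cannot be assessed. Removing the exception loses no child whom section 11.0 admits.

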**12.0 Vulnerable Populations: Individuals who are not yet adults (infants, children, teenagers)**

*12.1 Adequate provisions have been made for soliciting the permission of parents or guardians as well as for soliciting the assent of children. Lumason is FDA approved for the use in the pediatric population to identify other abdominal abnormalities, specifically focal liver lesions. The intervention presents an experience that is reasonably commensurate with that inherent in the subjects medical situation, and is likely to yield generalizable knowledge about the condition, which is of vital importance for the amelioration of pediatric appendicitis.*

**13.0 Local Number of Subjects**

*13.1 This study will enroll 250 subjects. Assuming an accrual rate of 15-20 subjects per month, we estimate it will take 12-15 months to complete enrollment.*

*13.2 Based on prior data, approximately 375 children are diagnosed with appendicitis at our institution per year. We plan to screen up to 750 potential subjects for eligibility over the course of the study.*

**14.0 Screening and Recruitment Methods**

*14.1 Potential subjects will be recruited in their hospital room, ED, or radiology department by a member of the general surgery team. Per standard of care, the general surgery team will be alerted by the emergency department when*

a patient presents with concern for acute appendicitis. The general surgery staff will screen for eligibility criteria. Those meeting all inclusion and no exclusion criteria will be invited to participate. PAC will be obtained on either a paper or electronic form.

- 14.2 The source of subjects will be the CMH Adele Hall campus emergency department.
- 14.3 Potential subjects will be identified when, per standard of care, the general surgery team is alerted by emergency department staff of a patient presents with concern for acute appendicitis. The general surgery staff will screen for eligibility criteria. Those meeting all inclusion and no exclusion criteria will be invited to participate.
- 14.4 A pre-screening log will be maintained for the purpose of tracking enrollment. Patients who are referred to the department of surgery for concern of acute appendicitis will have the date of referral, DOB, MRN, PAS, whether or not they met inclusion, were approached for participation and their choice to participate recorded on the pre-screen log. We are requesting a Waiver of HIPAA Authorization for recruitment purposes only. The PHI recorded on the screening log will help ensure required reporting elements at time of study publication, including the percentage of eligible patients enrolled and reasons patients decline enrollment. The pre-screen log will be destroyed at the conclusion of the study.

14.5 N/A

14.6 N/A

## **15.0 Reimbursement, Payment and Tangible Property provided to subjects**

N/A

## **16.0 Withdrawal of Subjects**

- 16.1 As this study consists of a one-time intervention, we do not anticipate any circumstance in which a subject will be withdrawn without their consent.
- 16.2 Subjects may choose to discontinue study participation at any time, for any reason, specified or unspecified, and without prejudice. Subjects may be discontinued from the study for any of the following reasons:
  - At the subject's or their parent's/LAR's request
  - At the discretion of the site investigator as deemed appropriate for any reason

Procedures for orderly termination will include a discussion with the parents or LAR for the reasons behind early termination.

16.3 If a subject withdraws from the research study, data that has already been collected may still be used; however, no new information will be collected except information related to adverse events or other safety issues.

## 17.0 Risks to Subjects

17.1 As part of SOC, all patients enrolling in this study will have at least one functioning intravenous catheter placed during the SOC blood draw, hence no new IV access will be required. We expect that there may be some mild discomfort related to the performance of the ultrasound study itself and will monitor for this. Other than the discomfort from the ultrasound probe, we do not expect any other ultrasound-related discomfort. Patients will be monitored by licensed personnel during the study interval. Per standard of care, patients will return to the ED while the results of their gray scale ultrasound and CT, if one was taken, are obtained. ED staff will continue to monitor patients for any adverse event.

Reported risks related to Lumason administration include:

Adverse Reaction	Number	(%)
Any Adverse Reaction	340	5
Headache	65	1
Nausea	37	0.5
Dysgeusia	29	0.4
Injection site pain	23	0.3
Feeling hot	18	0.3
Chest discomfort	17	0.2
Chest pain	12	0.2
Dizziness	11	0.2
Injection site warmth	11	0.2

Serious cardiopulmonary reactions, including fatalities, have occurred uncommonly in adults during or shortly following administration of ultrasound contrast agents, including Lumason. These reactions typically occurred within 30 minutes of administration. Hypersensitivity reactions such as skin erythema, rash, urticaria, flushing, throat tightness, dyspnea, or anaphylactic shock have uncommonly been observed following the injection of Lumason. The exclusion criteria eliminate any subjects with a known cardiac abnormality or a known sensitivity to sulfur hexafluoride, so we do not anticipate that these reactions will occur. Resuscitation personnel and equipment will be available during the study treatment and follow-up period.

17.2 This study poses a minor increase over minimal risk as Lumason will be used off-label, but the intervention presents an experience that is reasonably commensurate with those inherent to the subject's medical situation. The only risks attributable to the study are those

of the adverse reactions listed above, as these patients will have already had an IV placed, and would have ultrasound as part of their appendicitis workup. Furthermore, Lumason is currently FDA approved, and in use at CMH, for other abdominal CEUS applications such liver lesions and vesicoureteral reflux in pediatrics.

17.3 N/A

17.4 N/A

17.5 N/A

## 18.0 Potential Benefits to Subjects

18.1 There is some possibility of potential benefit to subjects participating in this research. Although Lumason is not yet approved for use in diagnosing appendicitis, it is possible that the improved quality of US images produced will provide better information to providers treating these patients. It is also possible that the improved quality imaging could result in incidental findings, such as abdominal anomalies other than appendicitis. If such anomalies are found, the investigator could recommend to parents to follow up with appropriate services.

## 19.0 Investigator Assessment of Risk/Benefits Ratio: (IRB makes the final determination)

Select as applicable:	Pediatric Risk Category:	
	Category 1	Research not involving greater than minimal risk (45 CFR §46.404 and 21 CFR §50.51)
X	Category 2	Research involving greater than minimal risk but presenting the prospect of direct benefit to the individual subjects. (45 CFR §46.405 and 21 CFR §50.52)
	Category 3	Research involving greater than minimal risk and no prospect of direct benefit to individual subjects, but likely to yield generalizable knowledge about the subject's disorder or condition. (45 CFR §46.406 and 21 CFR §50.53)
	Category 4	Research not otherwise approvable which presents an opportunity to understand, prevent, or alleviate a serious problem affecting the health or welfare of children. (45 CFR §46.407 and 21 CFR §50.54)
Select if applicable:	Adult Risk Category:	
	Not Greater than Minimal Risk	
	Greater than Minimal Risk	

